6.3.1. Liver chemistry stopping and follow-up criteria

Increased Liver Chemistries

Eltrombopag administration may cause hepatotoxicity. In the ITP controlled clinical studies, one patient experienced Grade 4 (NCI Common Terminology Criteria for Adverse Events [NCI CTCAE] toxicity scale) elevations in serum liver test values during therapy with eltrombopag, worsening of

underlying cardiopulmonary disease, and death. No patients in the placebo group experienced Grade 4 liver test abnormalities. Overall, serum liver test abnormalities (predominantly Grade 2 or less in severity) were reported in 10% and 8% of the eltrombopag and placebo groups, respectively. In the controlled studies, two patients (1%) treated with eltrombopag and two patients in the placebo group (3%) discontinued treatment due to hepatobiliary laboratory abnormalities. Seven of the patients treated with eltrombopag in the controlled studies with hepatobiliary laboratory abnormalities were re-exposed to eltrombopag in the ITP extension study. Six of these patients again experienced liver test abnormalities (predominantly Grade 1) resulting in discontinuation of PROMACTA in one patient. In the ITP extension study, one additional patient had eltrombopag discontinued due to liver test abnormalities (all \leq Grade 3).

Serum ALT, AST, and bilirubin should be measured prior to initiation of eltrombopag, every 2 weeks during the dose adjustment phase and monthly following establishment of a stable dose. If bilirubin is elevated, perform fractionation. Evaluate abnormal serum liver tests with repeat testing within 3 to 5 days. If the abnormalities are confirmed, monitor serum liver tests weekly until the abnormality(ies) resolve, stabilize, or return to baseline levels.

Once more than six patients are enrolled in the study: The study will be stopped if 33% of the patients develop any of the following labelled hepatotoxicity monitoring criteria for drug cessation.

Treatment with eltrombopag should be discontinued because of abnormal liver tests if any of the following 4 conditions apply:

- ALT levels \geq 3 times upper limit of normal (ULN) and bilirubin levels \geq 1.5 times ($>$ 35 % conjugated bilirubin) ULN,
- (2) ALT levels \geq 3 times ULN and appearance or worsening of hepatitis symptoms or rash,
- (3) ALT levels remain \geq 3 times ULN for $>$ 4 weeks, or
- (4) ALT levels are \geq 5 times ULN.
- If a subject has an adverse experience that would, in the investigator's judgment, make continued participation in the study an unacceptable risk
- Note: If the subject's ALT and bilirubin levels decrease so that both are \leq 1.5 times ULN, the investigator may decide to restart the medication and monitor on a weekly basis.

Exercise caution when administering PROMACTA to patients with hepatic disease. Use a lower starting dose (0.3-0.4 mg/kg) of PROMACTA in patients with moderate to severe hepatic disease and monitor closely.

6.4. Adverse Events

The investigator or site staff will be responsible for detecting, documenting and reporting events that meet the definition of an AE or SAE.

6.4.1. Definition of an AE

Any untoward medical occurrence in a patient or clinical investigation subject, temporally associated with the use of a medicinal product, whether or not considered related to the medicinal product.

Note: An AE can therefore be any unfavorable and unintended sign (including an abnormal laboratory finding), symptom, or disease (new or exacerbated) temporally associated with the use of a medicinal product. For marketed medicinal products, this also includes failure to produce expected benefits (i.e. lack of efficacy), abuse or misuse.

Events meeting the definition of an AE include:

- Significant or unexpected worsening or exacerbation of the condition/indication under study.
- Exacerbation of a chronic or intermittent pre-existing condition including either an increase in frequency and/or intensity of the condition.
- New conditions detected or diagnosed after investigational product administration even though it may have been present prior to the start of the study.
- Signs, symptoms, or the clinical sequelae of a suspected interaction.
- Signs, symptoms, or the clinical sequelae of a suspected overdose of either investigational product or a concurrent medication (overdose per se should not be reported as an AE/SAE).
- “Lack of efficacy” or “failure of expected pharmacological action” per se will not be reported as an AE or SAE. However, the signs and symptoms and/or clinical sequelae resulting from lack of efficacy will be reported if they fulfill the definition of an AE or SAE.

Events that do not meet the definition of an AE include:

- Medical or surgical procedure (e.g., endoscopy, appendectomy); the condition that leads to the procedure is an AE.
- Situations where an untoward medical occurrence did not occur (social and/or convenience admission to a hospital).
- Anticipated day-to-day fluctuations of pre-existing disease(s) or condition(s) present or detected at the start of the study that do not worsen.
- The disease/disorder being studied, or expected progression, signs, or symptoms of the disease/disorder being studied, unless more severe than expected for the subject’s condition.

6.4.2. Definition of a SAE

A serious adverse event (SAE) is any untoward medical occurrence that, at any dose:

- a. Results in death
- b. Is life-threatening

NOTE: The term 'life-threatening' in the definition of 'serious' refers to an event in which the subject was at risk of death at the time of the event. It does not refer to an event, which hypothetically might have caused death, if it were more severe.

- c. Requires hospitalization or prolongation of existing hospitalization

NOTE: In general, hospitalization signifies that the subject has been detained (usually involving at least an overnight stay) at the hospital or emergency ward for observation and/or treatment that would not have been appropriate in the physician’s office or out-patient setting. Complications that occur during hospitalization are AEs. If a complication prolongs hospitalization or fulfills any other serious criteria, the event is serious. When in doubt as to whether “hospitalization” occurred or was necessary, the AE should be considered serious. Hospitalization for elective treatment of a pre-existing condition that did not worsen from baseline is not considered an AE.

d. Results in disability/incapacity, or

NOTE: The term disability means a substantial disruption of a person's ability to conduct normal life functions. This definition is not intended to include experiences of relatively minor medical significance such as uncomplicated headache, nausea, vomiting, diarrhea, influenza, and accidental trauma (e.g. sprained ankle) which may interfere or prevent everyday life functions but do not constitute a substantial disruption.

e. Is a congenital anomaly/birth defect

f. Medical or scientific judgment should be exercised in deciding whether reporting is appropriate in other situations, such as important medical events that may not be immediately life-threatening or result in death or hospitalization but may jeopardize the subject or may require medical or surgical intervention to prevent one of the other outcomes listed in the above definition. These should also be considered serious. Examples of such events are invasive or malignant cancers, intensive treatment in an emergency room or at home for allergic bronchospasm, blood dyscrasias or convulsions that do not result in hospitalization, or development of drug dependency or drug abuse.

g. All Grade 4 laboratory abnormalities assessed using the National Cancer Institute (NCI) Common Terminology Criteria for Adverse Events (CTCAE) v3.0 Common Terminology Criteria for Adverse Events (v 3.0)] except Grade 4 thrombocytopenia.

h. Ocular events of clinical concern.

Note: All serious adverse events will be followed until resolution of the events or definitive conclusion.

6.4.3. Disease-Related Events and/or Disease-Related Outcomes Not Qualifying as SAEs

During the assessment period, thrombocytopenia that results in administration of rescue treatment does not qualify as an AE or SAE. Also during this assessment period, hospital admissions that are attributable to such treatment failures or related therapy also do not qualify as AEs or SAEs. Hemorrhagic complications of thrombocytopenia not otherwise meeting regulatory serious criteria will be reported as AEs.

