- Accompanied by clinical symptoms of liver injury or evidence for hepatic decompensation.

Bone Marrow Reticulin Formation and Risk for Bone Marrow Fibrosis

Eltrombopag is a thrombopoietin (TPO) receptor agonist and TPO-receptor agonists may increase the risk for the development or progression of reticulin fiber deposition within the bone marrow.

In the ITP extension study, seven patients had reticulin fiber deposition reported in bone marrow biopsies, including two patients who also had collagen fiber deposition. The fiber deposition was not clearly associated with cytopenias and did not necessitate discontinuation of eltrombopag. However, clinical studies have not yet excluded a risk of bone marrow fibrosis with cytopenias and discontinuation of eltrombopag.

Prior to initiation of eltrombopag, examine the peripheral blood smear closely to establish a baseline level of cellular morphologic abnormalities. Following identification of a stable dose of eltrombopag, examine peripheral blood smears and CBCs monthly for new or worsening morphological abnormalities (e.g., teardrop and nucleated red blood cells, immature white blood cells) or cytopenia(s). If the patient develops new or worsening morphological abnormalities or cytopenia(s), discontinue treatment with eltrombopag and consider a bone marrow biopsy, including staining for fibrosis.

Worsened Thrombocytopenia After Cessation of Eltrombopag

Discontinuation of eltrombopag may result in thrombocytopenia of greater severity than was present prior to therapy with eltrombopag although this is only seen in a minority of patients who stop the drug. This worsened thrombocytopenia may increase the patient's risk of bleeding, particularly if

eltrombopag is discontinued while the patient is on anticoagulants or antiplatelet agents. In the controlled ITP clinical studies, transient decreases in platelet counts to levels lower than baseline were observed following discontinuation of treatment in 10% and 6% of the eltrombopag and placebo groups, respectively. Serious hemorrhagic events requiring the use of supportive ITP medications occurred in 3 severely thrombocytopenic patients within one month following the discontinuation of eltrombopag; none were reported among the placebo group.

Following discontinuation of eltrombopag, obtain weekly CBCs, including platelet counts for at least 4 weeks and consider alternative treatments for worsening thrombocytopenia, according to current treatment guidelines

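### Section 6.4.3 takes rescued thrombocytopenia and related admissions out of AE and SAE reporting for an undefined period, in conflict with 6.4.1, 6.4.2(c) and 6.4.6

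*Combined protocol and SAP*

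**What the plan says.** Section 6.4.3 sets two exclusions. The first covers the low count itself: "During the assessment period, thrombocytopenia that results in administration of rescue treatment does not qualify as an AE or SAE". The second covers admissions: "hospital admissions that are attributable to such treatment failures or related therapy also do not qualify as AEs or SAEs". Bleeding is kept in: "Hemorrhagic complications of thrombocytopenia not otherwise meeting regulatory serious criteria will be reported as AEs".

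The general definitions point the other way. Section 6.4.1 lists as an AE "Significant or unexpected worsening or exacerbation of the condition/indication under study", and it sets aside signs of the studied disease only "unless more severe than expected for the subject’s condition". Section 6.4.2(c) makes an event serious if it "Requires hospitalization or prolongation of existing hospitalization". Section 6.4.2(g) makes Grade 4 laboratory abnormalities serious, "except Grade 4 thrombocytopenia", and puts no time limit on that exemption. Section 6.4.6 requires SAEs up to 30 days after the last dose to be reported regardless of causality, and to reach the manufacturer within 24 hours.

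Section 6.3 names the risk concerned: "Discontinuation of eltrombopag may result in thrombocytopenia of greater severity than was present prior to therapy with eltrombopag". It cites below-baseline falls after stopping in 10% of eltrombopag and 6% of placebo patients in the ITP studies, and serious hemorrhage within a month of stopping in 3 eltrombopag patients and no placebo patients.

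**The concern.** The exclusion in 6.4.3 depends on whether rescue was given, not on how the count compares with the patient's own starting level. A count that never rose and a count that fell well below baseline are therefore treated alike once rescue is given. The first is lack of efficacy. The second is, in the protocol's own account, a possible effect of stopping the drug.

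The classification has practical consequences. The 24-hour report in 6.4.6 is triggered by SAE status, the safety analysis in 8.3.1.2 counts patients with AEs and SAEs, and 6.3 describes the DSMB's interim assessment as one of AEs. An admission classed as neither leaves all three routes. With 15 treated patients and no control arm, one omitted serious event changes the safety picture.

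**Working it through.** The plan states no figure on this point. It turns on definitions, so the check applies each rule to the same case.

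**Case A: the count falls below the pre-treatment level, there is no bleeding, rescue is given and the patient is admitted.**
- 6.4.1: an AE, as worsening of the condition. The carve-out for expected disease does not apply if the fall is more severe than expected.
- 6.4.2(c): serious, because of the admission. The relief there is for elective treatment of a condition that has not worsened since baseline, and doubt about hospitalization is resolved toward serious.
- 6.4.2(g): gives no separate route, since a Grade 4 platelet count is exempt.
- 6.4.6: as an SAE, reportable within 24 hours, up to 30 days after the last dose.
- 6.4.3: neither AE nor SAE, if the case falls in the assessment period.

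The same patient receives two classifications. Section 6.4.3 is the more specific rule, so site staff would reasonably follow it. The conflict with 6.4.6 is indirect: 6.4.6 acts only on events already classed as SAEs, so 6.4.3 decides whether it is reached.

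**Case B: an admission for a complication of the rescue therapy.** The *related therapy* wording in 6.4.3 excludes it. Yet 6.4.2(c) treats complications arising in hospital as AEs, and 6.4.6 collects SAEs related to a concurrent medication. This conflict does not depend on withdrawal of the drug.

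**Does the assessment period reach past withdrawal?** The term occurs only in 6.4.3. The nearest wording is the 4-to-12-week assessment window in 8.3.1.1. Even on that reading, a patient who stops early under 4.4, 4.4.2 or 6.3 could have the post-withdrawal fall inside the window. The text does not settle the question.

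**What is captured elsewhere?**
- Rescue use and bleeding are collected and summarized (3.1).
- Blood counts continue for at least 4 weeks after stopping (6.1, 6.3).
- Exposure and laboratory values are summarized (8.3.1.2).
- The DSMB sees cumulative study data (6.4.8).

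The remaining gaps are these. Section 3.1 does not list admissions. Laboratory data are summarized by visit, but the schedule of events has no post-discontinuation visit. Section 6.4.7 does not name post-withdrawal thrombocytopenia among the other safety outcomes.

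**Scale.** Inputs are the 10% and 6% rates in 6.3 and the 15 treated patients in 3.1. The number n who stop is not given, so a range of 5, 10 and 15 is assumed, and ITP rates are assumed to apply to WAS/XLT. Expected falls = n × p; chance of at least one = 1 − (1 − p)^n.
- p = 0.10: expected 0.5, 1.0, 1.5; chance 1 − 0.9^5 = 41%, 1 − 0.9^10 = 65%, 1 − 0.9^15 = 79%.
- p = 0.06: expected 0.3, 0.6, 0.9; chance 1 − 0.94^5 = 27%, 1 − 0.94^10 = 46%, 1 − 0.94^15 = 60%.

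These are falls of any kind. The documents do not say what share would need rescue or admission, so the number that 6.4.3 would exclude cannot be derived.

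**The case against.** Thrombocytopenia is the disease here and the platelet count is the primary endpoint, so some disease-event exemption is a legitimate choice. Section 6.4.1 says that lack of efficacy as such is not an AE, and the reference in 6.4.3 to treatment failures suggests that inadequate response on drug was what its authors had in mind. On that view the period ends with treatment and post-withdrawal falls were never excluded. The serious post-withdrawal harm cited in 6.3 was hemorrhagic, and hemorrhage stays reportable.

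Much of this stands. It rules out a stronger reading that a reader might draw, namely that the plan conceals post-withdrawal thrombocytopenia. The exclusion is limited to a period that may not reach past withdrawal, and counts, rescue use and bleeding are recorded in any event. Nor does 8.3.1.2 confine the safety analysis to AEs and SAEs.

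A reader might also multiply 0.10 by 15 and conclude that one or two patients would go uncounted. That needs all 15 to stop, the ITP rate to carry over, every fall to be rescued, none to bleed, and the period to cover withdrawal. It also sets aside the 6% placebo rate: the difference is 4 points, or 0.04 × 15 = 0.6 patients.

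The objection does not remove the contradiction. If only lack of efficacy was meant, the text does not say so, and a fall below the patient's own baseline is not lack of efficacy. It also leaves the *related therapy* clause untouched.

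**Conclusion.** The point holds as a contradiction between reporting rules, made worse by an undefined term. Section 6.4.3 cannot be applied as written together with 6.4.1, 6.4.2(c) and, through them, 6.4.6.

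Two consequences follow, with different certainty. Whatever the length of the assessment period, 6.4.3 keeps admissions for related therapy within it out of the SAE counts. If, and only if, the period extends to the weeks after stopping, non-bleeding cases of a risk named in 6.3 can also be missing from the AE/SAE tables and the 24-hour reports.

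The size cannot be computed. Under the assumptions shown, about 0 to 2 post-withdrawal falls would be expected in the whole study, and those excluded would be some unknown part of them. That is small in number, but the change is worth making because single serious events carry weight in a group of 15.

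**What to change.** These changes concern reporting and tabulation only; they alter no treatment decision.

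1. Define the assessment period in 6.4.3 and state that it does not cover events after discontinuation.
2. Limit the exclusion to thrombocytopenia no worse than the patient's own baseline. Section 6.4.2(c) already uses worsening from baseline as its test for elective admissions.
3. Report admissions for below-baseline thrombocytopenia, or for complications of rescue therapy, as SAEs under 6.4.2(c).
4. Reconcile 6.4.3 with 6.4.1, 6.4.2 and 6.4.6, including the Grade 4 thrombocytopenia exemption in 6.4.2(g), which has no time limit.
5. Add to 8.3.1.2 and to the DSMB reports a table of rescue episodes, related admissions and post-discontinuation platelet counts, each set against the patient's baseline. Counts and rescue use are already collected; admissions would have to be added.

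The cost is a few more AE/SAE forms in 15 patients and one added table.

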6.4.4. Pregnancy

Pregnancy will not be allowed on study. Contraception must be used for all patients of child-bearing potential.

6.4.5. Time Period and Frequency of Detecting AEs and SAEs

Subjects will be given an adverse event sheet to complete at every study visit. This will help us to track any adverse events that have occurred and any medications that the subject has taken between visits. Subjects are instructed to notify the PI with any adverse events that he/she experiences.

6.4.6. Prompt Reporting of Serious Adverse Events and Other Events to NOVARTIS

Adverse events will be reported to the Investigational Review Board (IRB) as they occur and any

serious events will be reported to NOVARTIS within 24 hours of learning of the event if they occur. CTC criterion version 3.0 will be used as a guideline for reporting adverse events.

Any serious adverse events which occur during the clinical study or within 30 days of receiving the last dose of study medication, whether or not related to the study drug, must be reported by the investigator. In addition, any SAEs which occur as a result of protocol specific diagnostic procedures or interventions must also be reported.

All serious adverse events must be reported by facsimile or email within 24 hours to Novartis.

US CPO DS&E [contact]The SAE report should comprise a full written summary, detailing relevant aspects of the adverse events in question. Where applicable, information from relevant hospital case records and autopsy reports should be included. Follow-up information should be forwarded to NOVARTIS within 24 hours.

SAEs brought to the attention of the investigator at any time after cessation of eltrombopag and considered by the investigator to be related or possibly related to eltrombopag must be reported to NOVARTIS if and when they occur. Additionally, in order to fulfill international reporting obligations, SAEs that are related to study participation (e.g., procedures, invasive tests, change from existing therapy) or are related to a concurrent medication will be collected and recorded from the time the subject consents to participate in the study until he/she is discharged.

6.4.6.1. Regulatory reporting requirements for SAEs

The PI and/or data coordinator will be reporting unexpected serious adverse events promptly to the IRB and to NOVARTIS within 24 hours of learning of the event.

6.4.7. Other Safety Outcomes

Liver function tests, marrow reticulin, thromboembolism and other AE's will be tracked and reported.

6.4.8 Data Safety Monitoring Board

Weill Cornell Medical College requires that all research approved by the WCMC IRB include an appropriate plan for the monitoring of data to ensure the safety of human subjects. Research supported by Federal agencies will be monitored according to all regulations and guidelines of the relevant Federal agency.

The WCMC Data and Safety Monitoring Board (DSMB) will review the IRB approved protocol, informed consent documents, and data and safety monitoring plan. During the course of the study, the DSMB will review the cumulative study data semi-annually to evaluate safety, efficacy, study conduct, and scientific validity and integrity of the trial. The WCMC DSMB may also convene as needed if stopping criteria are met or other safety issues arise that the Principal Investigator and/or IRB would like the WCMC DSMB to address. The study PI will submit all written DSMB recommendations to the IRB upon receipt.

7. DATA MANAGEMENT

Case Report Form (CRFs) (see attached) will be filled out by the study coordinator using the raw data generated by study visits.

8. DATA ANALYSIS AND STATISTICAL CONSIDERATIONS

8.1. Hypotheses

The primary objective is to describe the pathophysiology of thrombocytopenia and bleeding in patients with Wiskott-Aldrich Syndrome (WAS) and determine the response to thrombopoietic agents *in vitro* and *in vivo*.

SPECIFIC AIMS:

1. To explore stem cell function in patients with WAS
2. To evaluate the functional state of circulating platelets in patients with WAS and relate it to clinical bleeding
3. To demonstrate whether a thrombopoietic agent, eltrombopag, administered daily will enhance stem cell function, increase platelet production and platelet count, and reduce bleeding in patients with WAS

